1.0 Objectives

1.1 Overview

Hematopoietic stem cell transplantation (HCT) is a commonly used and potentially curative treatment strategy for many hematologic malignancies.¹⁻⁴ Patients undergoing HCT usually receive high-dose chemotherapy followed by stem cell transplantation during a 3-4 week hospitalization.⁴⁻⁶ During this hospitalization, patients experience substantial physical symptoms with 50-70% reporting moderate to severe nausea, vomiting, fatigue, diarrhea, mucositis, and pain.⁷⁻¹² These symptoms, along with the physical isolation patients experience during their prolonged hospitalization, contribute to a dramatic deterioration in their quality of life (QOL) and mood throughout their hospital stay.¹¹⁻¹³ Notably, 40% of patients report clinically significant depression and anxiety symptoms during HCT.^{8,9,11} Furthermore, patients' experience during their transplant often leads to physical and psychological symptoms post-transplant, further exacerbating the morbidity of the procedure.^{8,13,14} Patients' caregivers (i.e. family and friends) also endure significant psychological distress as they witness their loved one struggle with the toxicities of HCT.^{15,16} Supporting a loved one through HCT not only causes considerable disruptions in the caregiver's personal life, but also leads to marked distress due to the patient's uncertain prognosis.^{11,16-18} Thus, patients and their caregivers struggle with the challenges of HCT, which negatively impacts their QOL and mood both during and after transplant.

Despite the tremendous burden experienced by patients undergoing HCT and their caregivers, studies of interventions to improve their QOL and reduce distress are lacking.^{7,11,19-21} Involvement of specialty-trained palliative care clinicians in the care of patients with advanced solid tumors has been shown to improve patient's QOL and mood and reduce their caregiver's psychological distress.²²⁻²⁷ Consequently, the early integration of palliative and oncology care is becoming the standard of care for patients with advanced solid tumors.²⁸ However, palliative care is rarely consulted to assist in the management of patients with hematologic malignancies.²⁹⁻³¹ Misconceptions equating palliative care with end-of-life care have contributed to the lack of involvement of palliative care for patients undergoing potentially curative therapy with HCT.²⁹⁻³³ However, given their extensive training and expertise in managing complex symptoms, palliative care clinicians are ideally positioned to treat the challenging toxicities experienced by this population.

We completed a single center randomized trial of inpatient integrated palliative and transplant care versus transplant care alone in patients with hematologic malignancies undergoing HCT (see Preliminary Studies).³⁴ Palliative care clinicians followed patients throughout their transplant hospitalization and conducted a minimum of two visits per week to 1) address patients' physical and psychological symptoms; 2) manage patients' and caregivers' expectations; and 3) provide both patients and caregivers with strategies to cope with the patients' illness and health status. Patients randomized to receive palliative care had a significant improvement in their QOL, symptom burden, depression, and anxiety during their hospitalization compared to those randomized to transplant care alone. Notably, the effects of the intervention were sustained three and six months post-HCT with significant improvements in depression, and post-traumatic stress symptoms.^{34,35} Caregivers also reported improvements in their coping and depression symptoms.³⁴ This was the first trial to establish the feasibility and preliminary efficacy of integrated palliative and transplant care in improving outcomes for patients with hematologic malignancies and their caregivers.

We propose to conduct a multi-site randomized trial of inpatient palliative care integrated with transplant care versus transplant care alone in patients with hematologic malignancies undergoing HCT. The primary goal of this study is to test the efficacy of inpatient palliative care integrated with transplant

PROTOCOL TITLE: Multi-Site Randomized Trial of Inpatient Palliative Care for Patients with Hematologic Malignancies Undergoing Hematopoietic Stem Cell Transplantation

care in improving patient- and caregiver-reported outcomes in a multi-site trial with a larger and more diverse patient population. We will also assess the impact of palliative care on participants' long term QOL and psychological outcomes. Data from this R01 will lay the foundation for a future implementation and dissemination trial of this care model.

Specific Aims

1. To demonstrate the efficacy of inpatient integrated palliative and transplant care for improving patient-reported QOL and psychological outcomes.

Hypothesis: Patients randomized to the intervention versus transplant care alone will report improved QOL and fewer depression and anxiety symptoms during their HCT and at 3, 6, and 12 months post-HCT.

2. To assess the impact of inpatient integrated palliative and transplant care on caregiver-reported QOL and psychological outcomes.

Hypothesis: Caregivers randomized to the intervention versus transplant care alone will report improved QOL and fewer depression and anxiety symptoms during patients' HCT and at 3, 6, and 12 months post-HCT.

3. To explore mediators and moderators of the effect of the integrated palliative and transplant care intervention on patient-reported QOL.

Hypothesis: Intervention effects on patient-reported QOL will be mediated by enhanced coping and reduced symptom burden in patients, and potentially moderated by patient demographic and clinical factors.

2.0 Background

Patients undergoing HCT experience immense physical and psychological symptoms

High dose chemotherapy followed by HCT is an intensive and potentially curative treatment for many patients with hematologic malignancies.¹⁻⁴ The use of HCT has increased recently due to data demonstrating its efficacy for new disease indications and acceptable safety profile in older patients.^{4,6} The majority of transplants in the United States are performed in the inpatient setting with patients receiving chemotherapy followed by stem cell transplantation during a 3-4 week hospitalization.⁵ Patients undergoing HCT experience substantial physical symptoms due to chemotherapy-induced toxicities and early post-transplant complications.⁷⁻¹² Studies show that 50-70% of patients undergoing HCT report moderate to severe nausea, vomiting, diarrhea, pain, insomnia, and fatigue.^{9,11} These symptoms, along with the physical isolation patients experience during the prolonged hospitalization, contribute to a rapid and dramatic deterioration in QOL and mood throughout the hospital stay.¹¹⁻¹³ Notably, 40% of patients report clinically significant depression and anxiety symptoms during HCT.^{8,9,11} Therefore, patients undergoing HCT have tremendous physical and psychological needs that may benefit from intensive supportive care measures to improve QOL and care.

Patients' experiences during hospitalization lead to physical and psychological symptoms post-HCT

Patients' physical and psychological symptoms during HCT have negative consequences on their long-term well-being.^{8,13,14} Studies demonstrate that patients' physical and psychological distress during HCT predicts their psychological morbidity and risk of transplant-related complications months after hospitalization.^{13,14,36} Many HCT survivors develop depression and post-traumatic stress symptoms as a result of their transplant experience.^{8,13,14,37} The extent of decline in patients' QOL and increase in depression symptoms during hospitalization strongly predicts their QOL impairment and risk of post-traumatic stress symptoms post-HCT.³⁸ As many as 41% of survivors experience post-traumatic stress symptoms up to 10 years post HCT.³⁹⁻⁴² These psychological complications further compound the morbidity of HCT. Thus, improving patients' symptoms and QOL during hospitalization for HCT may positively impact their QOL and psychological distress post-HCT.^{35,38}

PROTOCOL TITLE: Multi-Site Randomized Trial of Inpatient Palliative Care for Patients with Hematologic Malignancies Undergoing Hematopoietic Stem Cell Transplantation

Caregivers are also negatively impacted by patients' hospitalization for HCT

The family and close friends ("caregivers") of patients undergoing HCT are also impacted by the patient's illness.^{15,16} Stress from supporting a loved one through HCT and coping with an uncertain prognosis negatively affects caregivers' social and psychological well-being.¹⁶ Moreover, watching a loved one struggle with side effects during HCT can be emotionally challenging for caregivers.¹¹ Supporting a loved one through HCT often causes disruptions in the caregiver's personal life, including difficulty maintaining responsibilities at home and work.¹⁶⁻¹⁸ Thus, caregivers of patients undergoing HCT experience substantial caregiving burden, which negatively impacts their QOL and mood.^{15,43}

Interventions to address patients' symptom burden during hospitalization for HCT are lacking

Despite the substantial burden experienced by patients undergoing HCT and their caregivers, few studies have been conducted to improve their experience or outcomes.^{7,11,19-21} Investigators have examined the role of exercise and brief psychosocial interventions during HCT, demonstrating mixed results on patients' physical functioning, pain, and well-being.^{19,20,44,45} While a cognitive behavioral intervention in patients 1-3 years post-HCT reduced post-traumatic stress symptoms,⁴⁶ interventions targeting patients' and caregivers' psychological distress during HCT are lacking.¹¹ Further study is needed to address the physical and psychological symptoms experienced by patients undergoing HCT and their caregivers to enhance overall QOL and care.

Palliative care is underutilized but can address the complex needs of patients undergoing HCT

The 2016 American Society of Clinical Oncology Clinical Practice Guideline Update recommended palliative care from the time of diagnosis for all patients with metastatic solid tumors and/or high symptom burden.²⁸ This recommendation is based on several trials demonstrating improvements in QOL, symptom burden, mood, coping, and care delivery at the end of life for patients with advanced solid tumors receiving early palliative care.²²⁻²⁵ While palliative care is increasingly involved in the care of patients with advanced solid tumors, they are rarely consulted for patients with hematologic malignancies.²⁹⁻³¹ In a recent survey conducted by the American Society of Blood and Marrow Transplant, over 90% of transplant physicians reported that they do not collaborate frequently with palliative care clinicians.⁴⁷ Studies show that palliative care has not been well integrated with transplant care, due in part to misperceptions equating palliative care with end-of-life care and lack of evidence supporting the role of palliative care for patients being treated with curative intent.²⁹⁻³³ However, palliative care clinicians possess the expertise to manage complex symptoms and provide support for patients and their caregivers. Additionally, palliative care can support the transplant team by addressing concerns, fears, and expectations of patients and their caregivers during HCT.⁴⁸⁻⁵⁰ Integrating palliative and transplant care has great potential to improve outcomes for patients undergoing HCT and their caregivers.

[figure not shown]
Scientific Premise of the Proposed Project: Patients with hematologic malignancies undergoing HCT struggle with immense physical and psychological symptoms that negative impact their QOL and mood and contribute to long-term morbidity.^{7-14,37} Caregivers of patients undergoing HCT also endure substantial emotional distress during and after their loved one's transplant.^{15,16} Despite the burden experienced by these individuals, few interventions have been developed to improve their QOL and care.^{7,11,19-21} We completed a single center randomized trial of inpatient palliative care integrated with transplant care versus transplant care alone in patients with hematologic malignancies undergoing HCT.³⁴ We demonstrated statistically and clinically significant improvements in patients' QOL, symptom burden, depression, and anxiety (see Preliminary Studies).⁵¹ We also found that caregivers of patients randomized to the intervention reported significant improvement in coping and depression, compared to caregivers of those receiving transplant care alone.⁵¹ Importantly, the effects of the intervention were sustained three months and six months post-HCT with patients randomized to the intervention reporting significant improvements in their depression, and post-traumatic stress symptoms compared with those receiving transplant care alone.^{35,51} This study established the feasibility and preliminary efficacy of inpatient

PROTOCOL TITLE: Multi-Site Randomized Trial of Inpatient Palliative Care for Patients with Hematologic Malignancies Undergoing Hematopoietic Stem Cell Transplantation
 integrated palliative and transplant care to improve the QOL and care for patients with hematologic malignancies undergoing HCT and their caregivers.

These encouraging findings suggest that the next step in this programmatic line of research is to conduct a multi-site randomized trial to demonstrate definitively the efficacy of the intervention in improving patient- and caregiver-reported QOL and psychological distress and to establish the generalizability of the integrated care model across care settings. In addition, a large multi-site trial will enable us to explore potential mediators and moderators of the intervention effects to explore how the care model may be tailored to specific sub-populations. A 5-year study period will also allow us to assess the effects of the intervention on participants' long-term QOL and psychological outcomes. Importantly, this multi-site trial will provide the necessary data to overcome the barriers to integrating palliative care in the management of patients undergoing HCT and set the stage for future implementation and dissemination trial of this care model.

Conceptual Model: Our conceptual model in Figure 1 is adapted from a theoretical model of integrated palliative and oncology care for patients with solid tumors that is based on our team's prior research efforts.⁵² Patients' symptom burden during HCT hospitalization predicts psychological distress and QOL impairment post-HCT. The palliative care intervention will address patients' physical and psychological symptoms and both patients' and caregivers' expectations to enhance their coping during the hospitalization for HCT. Based on our prior data demonstrating changes in outcomes three and six months post-HCT, we anticipate that the intervention will lead to long-term improvements in participants' QOL and mood. As patients' symptoms and QOL during the HCT impact their caregivers' outcomes, we anticipate that the intervention will positively affect caregivers both directly by enhancing their coping and indirectly by improving patients' symptom burden and QOL.

Figure 1

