8.3 Exploratory endpoints

- Compare patient coping (Brief Cope) between the study groups

PROTOCOL TITLE: Multi-Site Randomized Trial of Inpatient Palliative Care for Patients with Hematologic Malignancies Undergoing Hematopoietic Stem Cell Transplantation

- Compare caregiver coping (Brief Cope) between the study groups
- Assess whether group differences in patient-reported QOL (FACT-BMT) are mediated by improved symptom burden (mediator: ESAS/HADS), or coping (mediator: Brief Cope)
- Assess whether patient or transplant related characteristics are moderators of the impact of palliative care intervention on patient-reported QOL

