10.0 Data and Specimen Banking: Not applicable

10.1 Data analysis

Specific Aim 1: To demonstrate the efficacy of inpatient integrated palliative and transplant care for improving patient-reported outcomes: Analyses will begin with descriptive and graphical summaries of the endpoints and evaluation of whether a normality assumption is reasonable for the endpoint or whether transformation is necessary. All statistical tests will be two-sided with an alpha level of 0.05. For all secondary and exploratory outcomes, we will use the false discovery rate (FDR) control method to address the issue of multiple testing. We selected an FDR of 0.15, which denotes the acceptable percentage of results that potentially represent false positives.⁶² The primary endpoint of the study will be to compare patient QOL (FACT-BMT) scores at week-2 between the study groups controlling for baseline values and demographic and clinical factors (as necessary for any imbalances in baseline variables) using a linear regression model. We will also compare secondary endpoints including patients' symptoms (ESAS), fatigue (FACT-Fatigue), depression and anxiety symptoms (HADS and PHQ9), and coping (Brief Cope) at week-2 between the study groups using linear regression models controlling for baseline values and clinical factors (as necessary for any imbalances in baseline variables). In the event that the effect of the intervention differs by transplant type, conditioning intensity, or other patient characteristics, we will examine these variables as interaction terms in the linear regression analyses. Finally, we will compute the effect size and Reliability Change Index to assess practical and clinical significance in the degree of change in the primary and secondary outcomes.

We will also utilize linear mixed models of the longitudinal data, allowing us to account for dependency among means over time and to control for demographic and clinical factors (as necessary for any imbalances in baseline variables) when examining change between groups in outcomes of interest across multiple time points (i.e., baseline, 2 weeks, 3, 6, and 12 months post-HCT). We will estimate practical and clinical significance of these outcomes (Cohen's d and Reliability Change Index).

Specific Aim 2: To assess the impact of inpatient integrated palliative and transplant care on caregiver-reported QOL and psychological outcomes: We will similarly compare caregivers' QOL

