PROTOCOL TITLE: Multi-Site Randomized Trial of Inpatient Palliative Care for Patients with Hematologic Malignancies Undergoing Hematopoietic Stem Cell Transplantation

(CARGOQOL), depression and anxiety symptoms (caregivers HADS and PHQ9), and coping at week-2 using linear regression models controlling for baseline values and clinical factors (as necessary for any imbalances in baseline variables). We will also use linear mixed models of the longitudinal data, allowing us to account for dependency among means over time and to control for demographic and clinical factors (as necessary for any imbalances in baseline variables) when examining change between groups in outcomes of interest across multiple time points (i.e., baseline, 2 weeks, 3, 6, and 12 months post-HCT). We will again estimate practical and clinical significance of these outcomes (using Cohen's d and Reliability Change Index).

Specific Aim 3: To explore mediators and moderators of the effect of the palliative care intervention on patient-reported QOL: We will conduct bootstrapped tests of mediation to determine whether group differences in patient-reported QOL (FACT-BMT) are mediated by improved symptom burden (mediators: ESAS/HADS), or coping (mediator: Brief Cope). Although in our randomized trial, we did not identify moderators of the effect of the palliative care intervention, we will test for potential moderators to ensure generalizability of our findings, as other studies have found age and gender as moderators of the impact of palliative care in patients with lung cancer.⁶³ We will create interaction terms for the linear regression analyses and linear mixed models to examine whether differences in patient-reported QOL are moderated by patient factors (age, gender, race), transplant factors (type of HCT, conditioning intensity), or study site.

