Although we observed a large effect size for our palliative care intervention on patient-reported QOL during hospitalization (primary endpoint, Cohen's d = 2.9), we chose to be conservative in estimating the sample size for this trial given the proposed testing of the effect of the intervention on caregivers and post-HCT outcomes, expected attrition over time, and the proposed tests of mediation and moderation. In our prior study, we observed a 6.9 point difference (SD = 20) in QOL at week-2 between intervention and control group. With a sample size of 360, we will have 87% power to detect at least 6.9 point difference in patient QOL at week-2 between groups with a two-sided 0.05 significance level and assuming 10% missing data at week-2. Importantly, we only had 2% and 6.9% missing data at week-2 and 3-months post-HCT in our prior study. With a sample size of 360, we will also have > 80% power to detect a treatment difference in secondary patient-reported outcomes at week-2 (symptom burden, depression, and anxiety) with a two-sided 0.05 significance level. Assuming a missing data rate of 15% at three and six months, we will have 80% power to detect a 4.3 point difference in patient-reported QOL at 3 and 6 months post-HCT between the two groups (based on the difference we detected in our previous study). In our prior trial, we enrolled 94 (56%) caregivers and we noted a 1.6-point difference (SD = 3.3) in caregiver HADS-depression scores between the two study groups at week-2. Assuming that we enroll caregivers

PROTOCOL TITLE: Multi-Site Randomized Trial of Inpatient Palliative Care for Patients with Hematologic Malignancies Undergoing Hematopoietic Stem Cell Transplantation

for 50% of the patients included in this study (n = 180), we will have 90% power to detect a 1.6-point difference in caregiver HADS-depression scores at week-2 between the two groups with a two-sided 0.05 significance level.

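### Interaction tests in 360 patients are too imprecise to ensure generalizability; effects by site and by transplant type should be estimated with intervals instead

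*Combined protocol and SAP*

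**What the plan says.** Section 2.0 (Background) says the next step is a multi-site trial to demonstrate efficacy definitively and "to establish the generalizability of the integrated care model across care settings". A separate sentence then says that a large trial will also allow mediators and moderators to be explored, with tailoring to sub-populations in view.

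Section 10.1, Aim 3, links moderators to generalizability directly: "we will test for potential moderators to ensure generalizability of our findings". The method is interaction terms in the linear regression and mixed models. The factors are age, gender and race, and "transplant factors (type of HCT, conditioning intensity), or study site". The same sentence concedes that "in our randomized trial, we did not identify moderators of the effect of the palliative care intervention", and cites age and gender effects seen elsewhere as grounds for testing anyway.

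Section 8.3 lists the analysis as exploratory: "Assess whether patient or transplant related characteristics are moderators of the impact of palliative care intervention on patient-reported QOL". Site is not named there. On error control, section 10.1 states "All statistical tests will be two-sided with an alpha level of 0.05" and, for secondary and exploratory outcomes, "We selected an FDR of 0.15".

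Section 10.2 gives 87% power for a 6.9-point main effect with 360 patients. Among its reasons for a conservative sample size it names "expected attrition over time, and the proposed tests of mediation and moderation". It gives no power and no detectable size for any interaction. The plan does not ask for site-specific or transplant-type-specific effects with confidence intervals, and it does not say how a non-significant interaction will be interpreted.

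**The concern.** A significance test can ensure generalizability only if a non-significant result counts in its favour. That is reasonable only when the test would probably detect a difference that matters, or when the interval around the interaction excludes one. The plan provides for neither. The trial is sized on the overall difference, and an interaction is estimated much less precisely than a main effect from the same patients.

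At stake is a secondary but prominent conclusion. The protocol presents the trial as the foundation for a dissemination and implementation study. A site or transplant type with little or no benefit could sit behind a positive average and a non-significant interaction. The primary comparison itself is not affected.

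**Working it through.** **Inputs from the documents.** Section 10.2: 360 patients, SD 20, difference 6.9, 10% missing at week 2, two-sided 0.05. Section 3.0: 1:1 randomization, three sites, stratified by site and transplant type.

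**Assumed, not in the documents.** Equal site sizes (120 each, near the 120–140 local patients in section 22.0); exactly one site with no benefit; the effect at the other two sites; a baseline to week-2 correlation r of 0.5 or 0.7; a 50:50 split for a two-level factor.

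**Step 1: the plan's own figure.** Evaluable per arm: 180 × 0.9 = 162. SE of the main effect = 20 × √(2/162) = 2.22. Then 6.9/2.22 = 3.105, and power = Φ(3.105 − 1.96) = 87.4%. The stated 87% reproduces.

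**Step 2: site interaction, 2-df F test.** Evaluable per arm per site: 162/3 = 54. The noncentrality is λ = 54 × Σ(site effect − mean)² / (2 × 20²).

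- Scenario A, average kept at 6.9: effects 0, 10.35, 10.35. The sum of squares is 47.61 + 2 × 11.90 = 71.4, so λ = 54 × 71.4/800 = 4.82. Power is 48%.
- Scenario B, 6.9 at the two benefiting sites: effects 0, 6.9, 6.9, mean 4.6. The sum of squares is 21.16 + 2 × 5.29 = 31.7, so λ = 54 × 31.7/800 = 2.14. Power is 24%.

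**Step 3: baseline adjustment.** The planned regression adjusts for baseline, so λ is divided by 1 − r². In A this gives 4.82/0.75 = 6.43 and 4.82/0.51 = 9.45. In B it gives 2.14/0.75 = 2.86 and 2.14/0.51 = 4.20.

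Chance that the site test at 0.05 misses the no-benefit site:

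| | Unadjusted | r = 0.5 | r = 0.7 |
|---|---|---|---|
| A (10.35 at the other two) | 52% | 39% | 21% |
| B (6.9 at the other two) | 76% | 70% | 57% |

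**Step 4: multiplicity.** Applying Benjamini-Hochberg at 0.15 across the six moderators, with the other five null and independent and no baseline adjustment, the simulated miss rates are about 59% (A) and 82% (B).

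**Step 5: precision of the estimates.**

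- One site's effect: SE = 20 × √(2/54) = 3.85, so the 95% CI is ±7.5 points. With adjustment it is 7.5 × √0.75 = ±6.5 or 7.5 × √0.51 = ±5.4.
- No-benefit site against the other two: SE = √(800/54 + 800/108) = 4.71, so ±9.2 unadjusted.
- Two-level factor split 50:50: SE = 2 × 2.22 = 4.44, so ±8.7 unadjusted. An interaction as large as the whole 6.9-point design effect has 34% power.

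**The case against.** The best defence is that the moderator work is labelled exploratory in the aims and in section 8.3, and that section 10.2 claims no power for it. Low power for interactions is usual in a trial sized on its main effect. Section 2.0 attaches generalizability to the multi-site design and attaches moderators to tailoring. The interaction models are already planned, so the gap could be called one of reporting. All of this is fair, and it limits the point to Aim 3 and the sample-size rationale. It does not settle the matter: Aim 3 itself gives generalizability as the reason for the tests, and nothing says how a null result will be read.

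Three stronger readings are tempting, and the documents do not support them.

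- A reader might infer that a null interaction will be declared proof of generalizability. No such rule exists; the wording only invites it.
- A reader might infer that the prior trial's lack of moderators is already used as support. The sentence is concessive: it notes that result and then explains why moderators will be tested anyway.
- A reader might take one miss rate, such as about half, as a property of the design. It holds only for Scenario A, unadjusted, at 0.05. Scenario B is harsher, but its average of 4.6 is below the planned effect, and the primary comparison itself would then have only about 54% power.

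**Conclusion.** The point holds as a mismatch between the stated use of the moderator tests and what they can show. Across the scenarios above, the site test at 0.05 misses a no-benefit site 21% to 76% of the time, or up to about 82% with false discovery rate control. Only the most favourable combination (10.35 points at the other two sites and r = 0.7) comes close to 80% power, and even there non-significance would not establish consistency. The unadjusted interval for one site (±7.5) is wider on each side than the 6.9-point design effect; with adjustment it is ±6.5 to ±5.4.

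The SD, missing rate and design effect are the protocol's. Site sizes, the pattern of site effects and the baseline correlation are assumptions, so the range should be cited rather than any single figure. Naming moderation as a reason for a conservative sample size has no calculation behind it, because the 87% concerns the main effect alone.

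**What to change.** In section 10.1, Aim 3, replace testing for generalizability with estimation. From the arm-by-factor models already planned, report the week-2 FACT-BMT difference with its 95% CI for each site and for each transplant type, and each interaction contrast with its 95% CI. State that a non-significant interaction will not be taken as evidence of generalizability, and that the intervals show which differences between sites or transplant types remain compatible with the data.

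In section 10.2, remove moderation from the reasons given for a conservative sample size, since 360 is powered on the main effect only.

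No extra patients or data are needed, and randomization is already stratified by site and transplant type. The cost is some protocol wording, a few extra rows of output and a weaker claim about generalizability.
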